5.1 Description

The Attending Nurse will meet patients and their families within the first 24 hours of their admission to begin the integrated care process and follow them until discharge. If assigned to the attending nurse model, patients will be followed by her if they are transferred to another service or unit rather than drop out of the study. The attending nurse will record the tasks she completes with each patient and the time each task required. This record will then become a part of the patient's medical record.

The Attending Nurse will have, in addition to a BSN and RN, at least 5 years of experience managing stroke and other neuroscience patients at the Hospital of the University of Pennsylvania. Additionally, she will also have training specific to the role of attending nurse through mentorship by nurses who currently work in this role at our institutions and at other institutions.

5.2 Intervention Regimen

The attending nurse will spend 30 minutes to 45 minutes upon initial evaluation to determine the patients' goals, barriers, and needs. The amount of time spent with each subject following the initial visit will vary based on the patient. To limit the demands on the attending nurse, she will never carry a case load of more than 8 patients at a single time. If on an even-numbered weekday the attending nurse has 8 patients, than the subject will be assigned to the routine care arm of the trial. Patients who are assigned to the attending nurse model of care will be seen by that nurse on a daily (weekday) basis in addition to being cared for by their regular care team of physicians and rotating staff nurses. All staff nurses as well

as the attending nurse will participate in morning interdisciplinary table rounds in keeping with preexistent quality processes.

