3.1 General Design

We propose a phase III comparative effectiveness study to evaluate the added value of an attending nurse to the inpatient care of stroke patients compared to routine care. Both types of care are currently available on the inpatient Vascular Neurology service at the Hospital of the University of Pennsylvania as well as at other institutions. Currently, the nurse attending works randomly with patient she selects based on her availability.

In the standard model of inpatient nursing care, stroke education is provided largely in the form of pamphlets distributed to patients and their families. Patients are cared for by a team of physicians and staff nurses with access to social workers and case managers, however, staff nurses do not routinely round on their patients with other members of the care team.

Screening of patients for this trial will occur once the clinical decision to admit a patient to the Vascular Neurology service has been made. All patients who meet inclusion criteria will be assigned to a study arm, addition of an attending nurse versus routine nursing care, according to the day of the week they are admitted to the hospital. Patients who are admitted on even numbered week days will have their care supplemented by the attending nurse. This is effectively a stratified random assignment, as there are no clinical or systematic features that otherwise are associated with odd or even numbered days. The duration of the intervention will depend on the duration of a patient's hospital admission.

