3.1.3 Allocation to Interventional Group

Stroke patients who are admitted on even-numbered weekdays and enrolled in this trial will be assigned to care with an attending nurse; patients admitted on odd-numbered weekdays will get usual routine care. The attending nurse will query the electronic medical record as well as communicate with the physician team so that all incoming admissions on even-numbered days to the Vascular Neurology service are known to the attending nurse.

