6.2 Study Intervention Phase

If patients satisfy inclusion criteria and lack exclusion criteria they will be assigned to the intervention arm or the control arm depending on their admission date. The intervention phase will be the duration of the patient's hospital stay.

No research related procedures that differ from standard of care will be conducted as this is a comparative effectiveness trial.

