7.5 Subject Population(s) for Analysis

The entire subject population who undergo treatment assignment will be studied primarily via intention to treat analysis comparing data from follow up phone calls between groups. An as-treated analysis will also be performed.

Analysis will be performed on some pre-defined subgroups where we may expect to see effect modification: major stroke vs. minor strokes (NIHSS \leq 5), multiple medications vs. few medications, patients who were admitted following a recurrent stroke vs. a new stroke, and hemorrhagic stroke vs. ischemic stroke subtypes.

8 Safety and Adverse Events

This protocol is extremely low risk as it assigns patients to already existent forms of inpatient care. This study does not include any experimental treatment. Given there is no proposed intervention or proposed management beyond two existing forms of standard clinical care, the routine collection of adverse events is not relevant, as those will be part of routine care. However, there may be a difference between the two arms in terms of specific events of interest. These specific events of interest include falls, aspiration pneumonia, and subsequent (post-discharge) major cardiovascular and cerebrovascular events (MACCE) including stroke (ischemic, hemorrhagic, or unknown), myocardial infarction, and death of any cause. Transfers to a higher level of care (e.g. to the Neuro ICU or medical ICU from the floor) that occur as part of routine care will also be considered events of interest. We will also report any unanticipated events.

All of the aforementioned events of particular interest will be assessed while the subject is in the hospital in keeping with standard clinical care. During follow up phone calls, the interviewee will ask patients and/or their family members specifically about the occurrence of MACCEs including and death of any cause.

The safety of each mode of nursing care while the subject is in-house will be tracked using the quality control processes that are already in place as part of standard inpatient care.

9 Study Administration, Data Handling and Record Keeping

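### Caseload overflow moves even-day patients into the control arm, so the intention-to-treat groups no longer follow the admission date on which comparability rests

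*Combined protocol and SAP*

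**What the plan says.** Three sections set the arm by the calendar alone.

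- Section 3.1 assigns patients "according to the day of the week they are admitted to the hospital" and then speaks of even-numbered weekdays. It defends the scheme on the ground that "there are no clinical or systematic features that otherwise are associated with odd or even numbered days".
- Section 3.1.3: "Stroke patients who are admitted on even-numbered weekdays and enrolled in this trial will be assigned to care with an attending nurse".
- Section 6.2: eligible patients "they will be assigned to the intervention arm or the control arm depending on their admission date". It gives no exception.

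Section 5.2 gives one. The attending nurse's caseload is capped at 8, and if on an even-numbered weekday she "has 8 patients, than the subject will be assigned to the routine care arm of the trial". Her list also includes patients who have left the unit, since under section 5.1 "patients will be followed by her if they are transferred to another service or unit rather than drop out of the study".

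On analysis, section 7.5 says "The entire subject population who undergo treatment assignment will be studied primarily via intention to treat analysis", and then "An as-treated analysis will also be performed". Section 7.4 specifies unadjusted t-tests and a Pearson chi-square test. Section 7.4.1 compares baseline variables and plans no adjustment.

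**The concern.** Section 5.2 changes the arm a patient is assigned to, not merely the care received. Read with section 7.5, an overflow patient is a control in the intention-to-treat analysis. Read with section 6.2 alone, the same patient belongs to the attending-nurse arm. The primary analysis set therefore depends on which section is followed.

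On the section 5.2 reading, the odd/even argument no longer covers the groups compared. The attending-nurse arm holds only patients admitted while a slot was open. The control arm holds odd-day patients from all periods, plus the even-day overflow. Full-list periods are represented in one arm only. If they differ in case mix, prognosis, calendar time or ward care, the difference enters the SPER and MMAS-4 comparisons as if it were a treatment effect. Because the list keeps transferred patients, long or complicated stays could fill it even when the ward is not busy.

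The as-treated analysis offers no check on this. An overflow patient is assigned routine care and receives routine care, so both analyses classify that patient identically. The plan has no overflow flag, caseload record or analysis by date.

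**Working it through.** **Inputs.** From the documents: cap of 8 (5.2); 700-800 admissions a year (4.5); 65% control adherence, a 15-point improvement, alpha 0.05, 80% power, 186 per arm, and a SPER difference of 0.3 with SD 2 (7.3). Assumptions: mean stay of 3, 5, 7 or 9 days; all admissions eligible; two-sided testing; 15% read as percentage points.

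**The plan's own figure.** n = [1.96·√(2·p̄·q̄) + 0.842·√(p₁q₁ + p₂q₂)]² / (p₂ − p₁)². With 65% vs 80% this is (1.238 + 0.524)² / 0.0225 = 138 per arm. The stated 186 does not follow from 80% power; it is close to the 185 needed for 90%. Both 186 and 138 are carried forward.

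**How often the list is full.** Even-weekday arrivals per day: (700 to 800)/365 × 5/7 × 1/2 = 0.685 to 0.783. Offered load a = rate × stay. Erlang-B with 8 places gives the overflow share (a⁸/8!) / Σ(aᵏ/k!), k = 0 to 8. A calendar simulation (Poisson weekday arrivals, entry on even dates only if fewer than 8 are on the list) checks this and also gives the share of the control arm admitted while the list is full.

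| Assumed stay | Even-day overflow, Erlang-B | Even-day overflow, simulated | Control arm admitted with list full | Attending-nurse arm |
|---|---|---|---|---|
| 3 days | 0.1-0.2% | 0.2-0.7% | 0.4-1% | 0% |
| 5 days | 1.5-3% | 2-4% | 3-6% | 0% |
| 7 days | 6-9% | 7-11% | 11-17% | 0% |
| 9 days | 13-18% | 14-19% | 22-29% | 0% |

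**Bias.** Let s be the control-arm share admitted with the list full, and d the outcome gap between full-list and open-list patients under the same care. The attending-nurse arm has no full-list patients, so bias = s × d.

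- SPER: to produce the 0.3 points of section 7.3, d must be 0.3/0.17 = 1.8 points (top of the 7-day range) or 0.3/0.29 = 1.0 point (top of the 9-day range). At 5 days it must be 0.3/0.06 = 5 to 0.3/0.03 = 10 points, on a scale with a maximum of 10.
- MMAS-4, no true effect, 10% overflow: 18.6 of 186 even-day patients move and the arms become about 167 and 205. Suppose overflow patients are 10 points less adherent than other even-day patients (56% vs 66%, keeping 65% overall). The control arm is then (186 × 65% + 18.6 × 56%)/204.6 = 64.2%, a spurious difference of 66.0 − 64.2 = 1.8 points, with type I error 6.5%. With a 20-point gap the figures are 3.6 points and 11.3%. These gaps are illustrations; the documents give none.

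**Cost of analysing by date.** If overflow patients gain nothing, the even-day rate is 65% + 15% × (1 − B), where B is the overflow share.

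| B | Power, 186 per arm | Power, 138 per arm | n per arm for 80% |
|---|---|---|---|
| 0 | 90.3% | 80.0% | 138 |
| 6% | 86.1% | 74.5% | 158 |
| 9% | 83.6% | 71.5% | 170 |
| 13% | 79.9% | 67.2% | 187 |
| 18% | 74.7% | 61.7% | 212 |

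**The case against.** The cap is a prespecified rule, triggered by a list that existed before the patient arrived rather than by that patient's condition. Nothing in the documents links a full list to outcome, so no bias is demonstrated. This stands: direction and size are unknown, and with no link the bias is zero.

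The larger shares come from assumed stays of 7 and 9 days. The SPER gaps needed there, 1.8 and 1.0 points, are 0.9 and 0.5 SD, and at 5 days or less a material SPER bias is hard to reach. This also stands. The 0.3-point yardstick is itself weak: with SD 2 and 186 per arm, power to detect it is only about 30%.

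Under section 6.2 taken literally, overflow patients stay in their date-assigned arm and the as-treated analysis would differ. That is correct, but it confirms that sections 5.2, 6.2 and 7.5 do not define one intention-to-treat population. Section 9.2 has dates of stay abstracted, so a by-date analysis is feasible among consenting patients. That makes the remedy cheap, but the plan does not call for the analysis.

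Finally, restricting both arms to open-slot admissions would avoid the dilution, so one could prefer it as primary. Analysis by date is the closer match to the plan's own argument for comparability and needs no caseload information, which is why it is placed first here.

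**Conclusion.** The concern holds and should be fixed. The documents contradict one another on how the arm is set. Under section 5.2 the primary groups depart from the admission date that alone justifies comparing them, and neither planned analysis would show it.

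The inconsistency is certain; the bias is conditional. Its size is the full-list share of the control arm multiplied by an outcome gap the documents do not give. That share is at most about 6% at stays of 5 days or less, where the issue is small, and about 11-29% at 7-9 days, where it could matter. These shares assume all 700-800 admissions are eligible; a lower eligible fraction reduces them. Since the overflow rate will be known only once the trial runs, the analysis rule should be fixed beforehand. Sections 5.5.1 and 9.3 have the data destroyed after analysis, so the grouping could not be corrected later.

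**What to change.** 1. In section 7.5, define the primary intention-to-treat groups by the odd or even weekday date that triggers allocation. Use one definition of that date, worded identically in sections 3.1, 3.1.3 and 6.2. Even-day overflow patients stay in the attending-nurse group for this analysis and count as routine care only in the as-treated analysis. Reconcile the wording of section 5.2 with this.
2. Record the nurse's caseload at every odd- and even-day admission, report the number of overflow patients, and add a sensitivity analysis limited in both arms to admissions made while a slot was open.

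The cost is wording in five sections and one logged number per admission. The caseload cap and the care delivered are untouched. The statistical price is dilution: with 186 evaluable per arm, MMAS-4 power stays near 80% up to about 13% overflow. With only 138 evaluable it falls below 80% at any appreciable overflow, so the sample size should be revisited once a local length of stay is available.

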5.3 Blinding

The 7, 30, and 90 phone surveys will be blinded to patients' group assignment. Staff nurses will not be blinded as to which patient the attending nurse is caring for. The PIs will not be blinded to subject treatment assignment as they will need to assure subject assignment is preformed correctly. Patients will not be formally blinded to their arm assignment, though patients may not realize that alternative models of care exist on the Vascular Neurology service. Waiving consent upon admission will help maintain patients' blinding. During the first follow up phone call, as part of the consenting process, we will specify that we are comparing different nursing styles of care. The interviewer preforming follow up phone calls and collecting data from the patient electronic medical record will be blinded to study group assignment.

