3.1.2 Study Intervention Phase

All of the standard medical care will be identical in both arms of the study. Health literacy will be assessed in all patients upon admission to assure educational interventions are directed accordingly. Patients who

are assigned to standard nursing care will receive standard care which includes educational interventions from staff nurses in keeping with current Joint commission and AHA/ASA guidelines. Patients assigned to routine care will not interact with the attending nurse. Patients who are assigned to the intervention will receive additional patient-centered supplementary care and education from the attending nurse.

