7.1 Primary Endpoint

The primary endpoint for this study will be a comparison of the mean scores on the SPER and the rate of adherence on the MMAS-4 (score < 2) and the SPER between groups at 7 and again at 90 days.

Scores on the MMAS-4 and SPER will be calculated per protocol. On the MMAS-4, affirmative answers will receive a point and negative answers will be assigned zero. The total score will be the sum of the answer to all four questions. The SPER, question 1 and 2 are scored as follows: 0 = no correct content in response to the question, 1 = the patient provided some but not all of the correct content in response to the question, and 2 = patient provided all key content in response to the question. Question 3-5 were scored as follows as 0 = no correct content in response to the question and 2 = the patient provided the correct response to the questions. A score of 10 indicates all correct responses to the key content.

The SIS is a patient-based, self-report scale in which each item is rated in a 5- point Likert scale in terms of the difficulty the patient has experienced in completing each item. A score of 1 = an inability to complete the item and a score of 5 = no difficulty experienced at all. Using an algorithm, summative scores are generated for each domain.

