9.2 Data Collection and Management

Data will be abstracted regarding demographics, medical/surgical history, stroke location, and dates of hospital stay. The results of follow-up phone calls will be recorded by the interviewer and directly inputted into the RedCap database. The database will be kept in RedCap prior to data cleaning. Hard copies of survey results will be kept in locked file cabinets.

Data will be managed and stored using REDCap, the software toolset and workflow methodology for electronic collection and management of research data, developed specifically around HIPAA-Security guidelines. REDCap (Research Electronic Data Capture) is a secure, web-based application that is flexible enough to be used for a variety of types of research. REDCap provides an intuitive user interface that streamlines project development and improves data entry through real-time validation rules (with automated data type and range checks). REDCap also provides easy data manipulation (with audit trails for reporting, monitoring and querying patient records) and an automated export mechanism to common statistical packages (SPSS, SAS, Stata, R/S-Plus). In addition to traditional data capture functionality, REDCap's survey capabilities are a powerful tool for building and managing online surveys. The research team can create and design surveys in a web browser and engage potential respondents using a variety of notification methods. All data collection projects rely on a thorough, study-specific data dictionary, defined by all members of the research team in an iterative, self-documenting process. This iterative development and testing process results in a well-planned and individualized data collection strategy.

The REDCap MySQL database is replicated in real time to a completely redundant instance of MySQL. The redundant instance is available for restoration of the primary database or for manual failover in the case of primary database failure. Time-stamped backup files are made from the replicated database daily by HUP Research Information Systems using automated backup routines.

Data and backups are stored in the HUP Research Information Systems Storage Area Network (SAN). Access to the SAN directories where data are stored will be limited to Research Information Systems personnel, with authentication performed using HUP's enterprise Active Directory service. De-identified data will be analyzed using STATA or SPSS.

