11.4 Informed Consent Process / HIPAA Authorization

A waiver of consent will be obtained for the initial intervention as detailed below. We will obtain informed consent using a verbal process, detailed below, for data abstraction from the medical record as well as follow up phone questionnaires at the 7 day phone call. We will thus request a waiver of written consent.

Consent will be obtained by the interviewer administering the questionnaires to the patient following verbatim a script approved by the IRB. Consent for all follow up phone surveys as well as chart abstraction from the inpatient stay will be obtained at the 7 day phone call. The consent process will take place over the phone. Subject privacy will be assured as all data will be stored securely and interviews will be conducted in private space.

Patients will be permitted to provide consent at the time of the consent discussion over the phone (e.g. verbal consent) given the low risks associated with this study. Patients can ask the interviewer to call back at a later time to avoid any coercion associated with time pressures. The subject will be informed that they can withdraw their consent at any point. Investigators will confirm that the patient understands the study by asking them if they have any questions or need any points clarified in keeping with the phone call transcript.

Documentation of informed consent (e.g. date and time, who obtained consent, who gave consent and subject ID number) will be made by the interviewer on the case report form as consent will be verbal. If the subject is unable to provide consent, their legally authorized representative may.

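### The interviewer said to be blinded also collects the chart data, and nothing keeps the chart closed until the day-90 SPER has been scored

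*Combined protocol and SAP*

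**What the plan says.** **Who does what.** Section 5.3: "The interviewer preforming follow up phone calls and collecting data from the patient electronic medical record will be blinded to study group assignment". Section 3.1 describes the caller as a trained research assistant with no part in inpatient care. Section 5.4 speaks of trained staff, also blinded.

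**What the chart contains.** Under 5.1 the attending nurse logs her tasks for each patient and the "time each task required. This record will then become a part of the" medical record. Section 3.1.2 (Study Intervention Phase): "Patients assigned to routine care will not interact with the attending nurse".

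**How the arm is set.** Even-numbered weekdays lead to the attending nurse, while "patients admitted on odd-numbered weekdays will get usual routine care" (3.1.3). There is one exception in 5.2: "If on an even-numbered weekday the attending nurse has 8 patients, than the subject will be assigned to the routine care arm".

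**What is abstracted, and from when.** Section 9.2: "Data will be abstracted regarding demographics, medical/surgical history, stroke location, and dates of hospital stay". Under 11.4, consent for "chart abstraction from the inpatient stay will be obtained at the 7 day phone call".

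**What is scored later.** The SPER is given at 7 and 90 days (6.3.1, 6.3.3) and is a primary endpoint at both (7.1). Questions 1 and 2 are graded 0, 1 or 2, where "1 = the patient provided some but not all of the correct content in response to the question". Questions 3 to 5 score 0 or 2.

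**The concern.** The blind in 5.3 is stated as a fact about a person, but the duties given to that person include opening a file that can show the arm. If the chart is opened between the 7-day and 90-day calls, the day-90 SPER may be scored by someone who knows the allocation. SPER questions 1 and 2 require the rater to decide whether a spoken answer is partly or fully correct, so both probing and scoring can drift with that knowledge. The MMAS-4, the 13 Likert questions, the health questions and the SIS are patient-reported and less exposed.

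A biased day-90 SPER would bear directly on one of the two primary measures. The sponsor itself relies on blinding as a reason for the initial waiver of consent (11.4.1.1).

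**Working it through.** The plan gives no figure to reproduce here. The point rests on the text, and the arithmetic only gives a sense of scale.

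**Can the chart reveal the arm?**
1. The nurse's record goes into the chart (5.1), and routine-care patients have no contact with her (3.1.2). Its presence therefore points to the intervention arm. Section 9.2 does not list the record for abstraction, but it lies in the same chart.
2. The dates of hospital stay (9.2) include the admission date. An odd weekday means routine care. An even weekday usually means the attending nurse, unless she already has 8 patients (5.2). The plan does not say whether the interviewer knows the rule.
3. Abstraction is unlikely to stop at a cover page. Baseline tables need stroke severity and history (7.4.1), and subgroups need NIHSS, number of medications and recurrent versus new stroke (7.5).

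**Is there time for it to matter?** Abstraction is allowed from the 7-day call. The nominal gap to the day-90 call is 90 − 7 = 83 days. With the Table 1 windows it runs from 76 − 10 = 66 to 104 − 4 = 100 days.

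**Does any safeguard close the route?** Staff outside inpatient care (3.1) protect independence. Case numbers on forms (5.4) and an identifier list held only by the PIs (9.2) protect identity. None of these blinds a person who opens the chart. No section sets an order, masks the record or names a separate abstractor.

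**Is there a second route?** Table 1 lists treatment allocation and the nurse's document as study items. Section 9.2 has the interviewer enter call results in REDCap and gives the research team access to the database. Whether those two items sit in REDCap, visible to the interviewer, is not stated.

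**Scale (illustration only).** Inputs from 7.3: SD 2 and 186 per arm. Assumptions: no true effect, no loss to follow-up, two-sided alpha 0.05, a mean scoring bias b in patients abstracted early, and a share f abstracted before the day-90 call.

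- SE = 2 × √(2/186) = 0.2074
- P(reject) = Φ(fb/SE − 1.96) + Φ(−fb/SE − 1.96)

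| | b = 0.1 | b = 0.2 | b = 0.3 |
|---|---|---|---|
| f = 1 | 0.077 | 0.161 | 0.304 |
| f = 0.5 | 0.057 | 0.077 | 0.112 |
| f = 0 | 0.050 | 0.050 | 0.050 |

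If the bias arises only in questions 1 and 2, b equals 2 × the net share of those ratings moved one level in one arm. The share is then b/2 = 5%, 10% or 15% among patients abstracted early, so the lower values of b are the more plausible.

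Loss to follow-up lowers the rates. With an assumed 30% loss, 186 × 0.7 ≈ 130 per arm, SE = 2 × √(2/130) = 0.248, and the largest entry falls from 30% to about 23%.

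**The case against.** The best defence is that this is an omission and not a contradiction. The plan states the blinding in 3.1, 5.3 and 5.4, nothing says abstraction comes before day 90, and the order of work often sits in a work instruction. This stands in part. A reader might infer that the blind will be broken, but the documents support only that nothing prevents it. It is still more than missing detail, because staff could follow the plan exactly and lose a blind that the plan claims.

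- **One person or several.** Section 5.4 speaks of staff, and 9.2 does not name the abstractor. If several people share the role, a patient's abstractor need not make that patient's day-90 call. This stands, and it lowers the likely number affected.
- **Other routes.** The first call tells patients that nursing styles are being compared (5.3), and the 13 questions cover the inpatient stay (6.3.1). Patients can therefore reveal their arm to the interviewer anyway. This stands, and it limits what any change to abstraction can gain.
- **Invented bias.** Both b and f are assumptions, and at b = 0.1 the rate is only 6–8%. This stands. A reader might take 30% as the trial's error rate, but no document gives a basis for that.
- **Day 7.** A reader might infer that the 7-day outcomes are compromised too. Chart consent is taken at that call, so they are not normally exposed. The reverse cannot be asserted flatly either: Table 1 places history and medications in the intervention phase, and the plan does not say who records them before consent.
- **Late consent.** Patients missed at day 7 are still called later (5.5). Those who first consent at day 90 cannot have been abstracted early.

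**Conclusion.** The concern holds in this form: the plan asserts a blinded interviewer but does not protect that blind for the day-90 SPER. Confidence is high that the text does not prevent early unblinding through the chart, and moderate that it would happen in practice. The number of patients affected is unknown.

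The size of any bias cannot be derived from the documents. The false-positive rates above depend on an assumed bias, an assumed share of charts opened early and complete follow-up, and they show only that a small scoring drift could matter. The finding does not establish that the blind is broken, that the 7-day results are affected or that the trial is invalid. It supports a cheap improvement that should be made.

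**What to change.** Add to 5.3 and 9.2:

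1. Nobody who will make a patient's later calls opens that patient's chart until the 90-day call is done or its window has closed (90 + 14 = day 104 after discharge, Table 1). A team member who makes no calls to that patient may abstract earlier.
2. Until then, the treatment-allocation and nurse-document items, if held in REDCap, are not visible to the interviewer.
3. Any clinical facts needed to score the SPER or to reach a proxy respondent come from a team member who is already unblinded, without the admission date or the nurse's record. The PIs are unblinded (5.3) and hold the identifier list (9.2).
4. State who records the Table 1 intervention-phase data before consent.

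Patients who agree to chart review alone have no later call and need no delay.

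**Cost.** A few sentences and a change in the order of work, with no extra staff under the delayed option. Chart data arrive 83 to 97 days after the 7-day call (90 − 7 and 104 − 7), about three months. This includes any events of interest (section 8) that are taken from abstraction. If those are wanted sooner, use an abstractor who makes no calls, at the cost of another person's time.

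**Limit.** This closes the chart and database routes only. Disclosure by patients on the calls remains, so the gain is partial and cannot be quantified from the documents.
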